1. INTRODUCTION AND REGISTRY RATIONALE

1.1 Proleukin for Cancer Therapy

Proleukin[®] (the brand name of aldesleukin for injection), also commonly known as interleukin-2 (IL-2) or recombinant IL-2 (rIL-2), was approved by US FDA in the 1990s for treating adult patients with metastatic Renal Cell Carcinoma (mRCC) or metastatic melanoma (mM). High dose IL-2 (hereafter “HD IL-2”) is the first immunotherapy approved for use as a single agent in the treatment of cancer. It appears necessary to create a profound systemic cytokine reaction to maximize tumor response^{1, 2}. Careful patient selection, hospitalization, and careful monitoring and management are mandatory for the administration of HD IL-2^{3, 4}.

As an immunotherapy, the IL-2 therapy aims to activate/stimulate a patient’s immune system by producing more cytotoxic T-cells to fight tumor or metastasized cancer cells⁵⁻⁷. However the exact mechanism by which the therapy mediates its antitumor activity in humans remains unclear and proper criteria allowing pre-therapy patient stratification for likelihood of response have not yet been established in clinical practice⁴.

To date, HD IL-2 is the only therapy for metastatic kidney cancer and melanoma that can produce a long lasting remission of disease. In the non-randomized small phase 2 trials from the approval of Proleukin to the modern era, the complete and overall response rates (CR and ORR) in treating melanoma and RCC were 5-6% and 15-28% respectively⁸⁻¹⁰. The most significant feature of these responses is the fact that the majority of CRs and a smaller proportion of Partial Responses (PRs) persist for years as measured by disease and treatment free survival, suggesting durable immunologic control or eradication of the malignancy. In these studies used for Proleukin approval, median Overall Survival (OS) of HD IL-2 was reported as 16-19 months for RCC but only 4.5-8.8 months for melanoma (data from a variety of trials reported prior to 2003)¹¹. Treatment-related death rates of HD IL-2 therapy were reported as 2% and 4% for melanoma and RCC respectively in the registration studies^{8, 9}. The follow-up for these studies is variable and is largely limited to the responder population¹². Subsequent reports of using HD IL-2 in these indications have been confounded by the following circumstances: a) selection bias; b) publication bias; c) small sample size; d) follow-up difficulty; e) frequent use of historical controls; f) combination drugs; and g) environment changes in medical practice. Therefore further data collection in the post-approval setting, e.g. a patient registry, is necessary to explore the use of the drug in the current environment.

Prognostic factors for HD IL-2 therapy are also controversial^{13, 14}. Predictive features including age, site and bulk of metastases, lactate dehydrogenase (LDH), hemoglobin etc., have been variable in their influence and subgroups are usually too small for reliable multivariate analysis. The clear cell carcinoma variant of renal cell and good performance status in both malignancies are reliable predictions of response in all studies.

1.2 Registry Rationale

Therapies requiring hospitalization and substantial expertise to administer, are difficult to evaluate utilizing the usual instrument, the randomized clinical trial, with endpoints of safety and effectiveness¹⁵. Blinding is impossible as comparative therapy does not require hospitalization or is so distinctly different that blinding is impossible.

The diseases treated in this manner are usually serious and often life threatening. Patient management, treatment outcomes, and safety are very dependent upon the experience of the hospital personnel. Evolving technologies and management strategies based on experience may greatly influence both safety and effectiveness but are likely to be individualized from site to site.

Registries have evolved as a method of investigating such therapies¹⁵, most notably, marrow and stem cell transplantation. By collecting observational data on all patients in a standardized way, the aforementioned challenges can be evaluated through both larger sample sizes and the ability to evaluate adequately sized cohorts of patients over various time periods with significantly different initial prognoses, management techniques or therapy combinations¹⁶. Prognostic factors hypothesized in small trials can be verified and refined using such a registry. Furthermore, the therapy's administration will become more standardized as it is studied and evolution will proceed more effectively.

The PROCLAIMSM Registry, is designed to create an observational database that will allow evaluations of the real world treatment patterns and trends involving HD IL-2 effectiveness, tolerability, and other patient management outcomes in treating patients with mRCC, mM or other malignancies in the United States (US).

2. REGISTRY OVERVIEW

2.1 Registry Design

The PROCLAIMSM Registry is a US-based, multicenter Registry designed to establish a high quality observational database of real-world clinical data on HD IL-2 when used to treat patients with mRCC, mM or other malignancies. The Registry will not, in any way, suggest changes in the treatment or management of the patients enrolled in the Registry. Therefore, physicians will continue to manage and treat patients according to standard of care and their own judgment.

The PROCLAIMSM Registry will start with a retrospective pilot data collection from a de-identified finite number of patient cases abstracted from their existing medical charts. The features collected will be identical to those planned for the prospective registry. The resulting database will be used to formulate hypotheses to be tested using the prospective registry database. Patients utilized in the retrospective analysis will be excluded from the prospective portion of the PROCLAIMSM Registry.

In the prospective portion of the Registry, sites will enroll patients who are expected to start a course of HD IL-2 therapy or have not yet completed their 1st course of HD IL-2

treatment. Once enrolled, the patient must receive at least one dose of HD IL-2 to remain in the Registry. Patients will be treated and followed according to the site's standard of care. This Registry will in no way induce changes in the management of individual patients. Clinical data features will be entered into an Electronic Data Capture (EDC) system, and organized into a registry database. The registry database will be interrogated according to database query protocols approved by the Steering Committee. (See **Appendix A** for an example data query proposal to the Registry Database). A subset of patients will participate in one of the Prometheus Proclivity studies (12PLK01, 12PLK02, 12PLK03). The Proclivity studies involve HD IL-2 in sequence with another therapy. Patients enrolled into any of the Proclivity studies and received a least one dose of HD IL-2 will be enrolled and followed in the Proclaim registry.

The data contained in the registry database will be observational data. The PROCLAIMSM Registry does not stipulate patient care, specific visits or interventions but merely surveys standardized parameters regarding HD IL-2 and associated therapies as they are applied by treatment centers. The collection of standard data over time permits the evaluation of trends in patient survival and subsequent therapy exposure. The database will be used to answer future queries formulated by researchers.

The PROCLAIMSM Registry will be sponsored by Prometheus Laboratories, Inc.

2.2 Registry Database Structure

The registry database will, contain individual patient demographic and clinical data as well as, data on the HD IL-2 treatment centers. This will include:

- Site specific practices in HD IL-2 administration
- Patient specific features
- Treatment emergent features
- HD IL-2 related outcomes
- Subsequent treatment

The Sponsor will be the sole custodian of the registry database. The Registry Steering Committee (RSC), a governance body of the PROCLAIMSM Registry, will be responsible for determining who has access to the data, what, and how the analyses are performed (see Section 7 "Queries of the Registry Database"). Section 7 also describes the process for releasing data from the registry database to querying investigators. The RSC is also responsible for determining if and when data will be extracted from the database or shared with others.

3. REGISTRY OBJECTIVES

3.1 Primary Objectives

- To establish a standardized source of observational data that can be used to report and query patient care patterns, clinical outcomes and trends from HD IL-2 therapy in treating mM, mRCC or other malignancies.

3.2 Secondary Objectives

- To create a retrospective database which can be used for hypothesis generation
- To report pre-specified summary data (see Section 6) on an annual basis

4. REGISTRY PLAN

4.1 Investigator Site Selection Criteria

Investigator sites will be included based on feasibility analysis of established medical centers where patients are treated with HD IL-2 by qualified physicians. Additional data on site characteristics, standard treatment approach, and volume of patients treated will be assessed. An adequate blend of high volume sites (sites that treat a minimum of 25 HD IL-2 patients per year) and low volume sites (sites that treat 5-15 HD IL-2 patients per year) as well as a representative distribution of patients with mM and mRCC, will be needed to participate in the Registry. Once sites are selected to participate in the Registry, the site physicians will enroll patients into the Registry. Treatment and follow up will occur per the site's standard of care.

The Registry is planned to include 25 sites in the US for prospective patient entry. Once the Registry procedures are established, additional sites may be added. Of the initial 25 planned sites, approximately 10 will apply the registry data collection instruments retrospectively to their HD IL-2 patients from several previous years, as a test of the system, and to create a separate database.

For retrospective participation, a site must have treated approximately 25 HD IL-2 patients in the previous year prior to participation in the Registry and have a medical record database that allows efficient retrospective data extraction (e.g., a qualified EMR system or research database). The PROCLAIMSM Registry will adjust the starting date for retrospective data collection to accrue an average of 25 consecutive patients at each site.

4.2 Selection of Patient Population

All eligible patients will be offered the opportunity to participate in the PROCLAIMSM Registry. Patients approached for participation who do not enter the registry will be recorded on the screening log with the reason for non-participation.

The PROCLAIMSM Registry will include approximately 250 patients in the retrospective cohort and a prospective cohort accrued over 5 years or longer.

4.3 Informed Consent

Prior to completing their 1st course of HD IL-2, patients will be provided information about participation in the Registry and must sign an Institutional Review Board (IRB) approved

informed consent document indicating their consent to participate. For patients that are participating in one of the Proclivity studies, 12PLK01, 12PLK02 or 12PLK03, it is acceptable for patients to sign consent for the Proclaim study at any time. The consent form must be signed by the patient or legal representative, and the investigator-designated site staff must obtain the consent. Documentation of consent must be maintained at the treating center. A copy will be provided to the patient and placed in the patient's medical record. Formal consent must be obtained before any prospective data collection occurs. No study data should be entered in the eCRFs until the patient has had at least one dose of HD IL-2.

Written consent is not required for the retrospective data collection as only de-identified patient data will be extracted from medical records of the patients who have conformed to site specific guidelines permitting research on their medical records without personal identification. Sites involved in the retrospective data collection are responsible for extracting and de-identifying patient data prior to data entry into the registry database. Prospective follow-up on surviving patients in the retrospective patient cohort will not be performed as this subset will not have been consented to participate.

4.4 IRB Approval of the PROCLAIMSM Registry

The PROCLAIMSM Registry protocol and its associated consent forms will be provided to registry sites. Sites are responsible for submitting the protocol and consent forms to their designated IRBs for review and approval. IRB approval must be documented prior to treatment facilities presenting the registry protocol to patients. Patient informed consent must be obtained prior to submission of data to the registry database.

4.5 Patient Inclusion/Exclusion Criteria

4.5.1 Inclusion Criteria

Patients who meet all of the following criteria will be eligible for inclusion into the Registry:

Prospective Cohort:

- 18 years of age and older
 - Given informed consent for participating in the Registry
- Is receiving or has received an initial course (2 cycles) of HD IL-2 and has not had post treatment imaging studies performed prior to enrollment. Data will only be collected and analyzed for patients who received at least one dose of HD IL-2. Exception: Patients enrolled in a Proclivity study (12PLK01, 12PLK02 or 12PLK03) can be enrolled into the registry at anytime.

Retrospective Cohort:

- 18 years of age and older
- Received HD IL-2 at the site prior to site initiation
- Have conformed to site specific guidelines permitting research on medical records without personal identification

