6. ANNUAL DATA OUTPUT SUMMARY

It is anticipated that a report will be generated on an annual basis in order to track the status of the registry database and have an executive summary on current use of IL-2 and outcomes. The following data will be included in the annual summary.

- Number of sites in the PROCLAIMSM Registry
- Number of patients enrolled (total, mM, and mRCC)
- Number of patients treated with HD IL-2 alone
- OS and PFS

- Investigator-determined ORR at 3-month assessment
- Number of dose per HD IL-2 treatment cycle
- Number of HD IL-2 cycles received per patient
- Causes of discontinuation of HD IL-2 treatment

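### Section 4.5.1 read literally bars a not-yet-enrolled patient who stopped after one cycle but admits a two-cycle completer; Sections 2.1 and 4.3 do the reverse

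*Protocol*

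**What the plan says.** Four sections of the protocol bear on who may enter the prospective cohort and until when.

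- **Section 4.5.1** (all criteria must be met) sets the criterion: "Is receiving or has received an initial course (2 cycles) of HD IL-2 and has not had post treatment imaging studies performed prior to enrollment". The same bullet adds: "Data will only be collected and analyzed for patients who received at least one dose of HD IL-2".
- **Section 4.5.2** excludes anyone who has had more than one course, and points back to 4.5.1 for what a course is.
- **Section 2.1** describes enrolment of "patients who are expected to start a course of HD IL-2 therapy or have not yet completed their 1st course of HD IL-2". It then sets the condition for staying in: "Once enrolled, the patient must receive at least one dose of HD IL-2 to remain in the Registry".
- **Section 4.3** fixes the timing of consent: "Prior to completing their 1st course of HD IL-2, patients will be provided information about participation in the Registry and must sign". Patients in a Proclivity study are exempt here and in 4.5.1, and may enter at any time.

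Section 6 lists the annual outputs. They include "Number of HD IL-2 cycles received per patient", causes of discontinuation, the 3-month response rate, OS and PFS.

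**The concern.** The registry's primary objective is a standardized source on care patterns, outcomes and trends. An entry rule that depends on how much treatment a patient got through selects on quantities that Section 6 reports, and no analysis can recover patients who were never enrolled.

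As worded, 4.5.1 has that feature for anyone approached after treatment has stopped. Sections 2.1 and 4.3 have it too, in the opposite direction. Sites that follow different sections would enrol different populations, and the annual summary would pool them.

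**Working it through.** **Side-by-side reading.** Take a patient outside the Proclivity studies, first approached after HD IL-2 has stopped and before any post-treatment imaging.

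| Section followed | Stopped for good after one cycle | Completed two cycles |
|---|---|---|
| 4.5.1 alone | Not admitted: no longer receiving, and has not received the 2-cycle course | Admitted by the second limb |
| 2.1 alone | Admitted: first course not completed | Not admitted |
| 4.3 alone | May still consent | Consent window closed |
| 4.5.1 and 4.3 together | Not admitted | Not admitted |

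In the last row the second limb of 4.5.1 has nobody left to admit, which shows that the sections were not written to one rule. Section 2.1 also enrols patients expected to start, for whom 4.5.1 has no limb.

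A patient enrolled under 2.1 before the first dose, or under either section during cycle 1, stays in after a single dose. Nothing removes that patient for stopping later. The conflict is confined to late entry.

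**Size.** The protocol states no figure on this point, so there is none to reproduce; the Appendix A sample size does not bear on it. Two unknowns drive the effect, and both are assumed here:

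- q, the share of patients who stop after one cycle;
- u, the share of those stoppers not yet enrolled when they stop.

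Also assumed: response rate 5% in one-cycle stoppers and 20% in everyone else, and exactly two cycles for everyone else.

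Under literal use of 4.5.1:

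- reported one-cycle share o = q(1 − u) / (1 − qu)
- reported response rate = 5%·o + 20%·(1 − o)
- reported mean cycles = 2 − o
- true response rate = 5%·q + 20%·(1 − q)

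At q = 20% the true response rate is 0.20 × 5% + 0.80 × 20% = 17.0%, and the true mean is 1.80 cycles.

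| u | One-cycle share reported | Response rate reported | Shift (points) | Mean cycles |
|---|---|---|---|---|
| 0 | 20.0% | 17.0% | 0 | 1.80 |
| 10% | 0.18/0.98 = 18.4% | 17.2% | 0.2 | 1.82 |
| 25% | 0.15/0.95 = 15.8% | 17.6% | 0.6 | 1.84 |
| 50% | 0.10/0.90 = 11.1% | 18.3% | 1.3 | 1.89 |
| 100% | 0% | 20.0% | 3.0 | 2.00 |

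For q from 10% to 30%, the response shift runs from 0.1 to 0.3 points at u = 10%, and from 1.5 to 4.5 points at u = 100%. At u = 50% the reported one-cycle share is 5.3% against a true 10%, and 17.6% against a true 30%.

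**Opposite direction.** Under 2.1 and 4.3 it is late-approached completers who are lost. With q = 20% and, as a further assumption, 10% of completers missed, o = 0.20 / (0.20 + 0.80 × 0.90) = 0.217. The reported response rate is 0.217 × 5% + 0.783 × 20% = 16.7%, a shift of about −0.3 points.

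**The case against.** A reader might infer that the criterion keeps early discontinuers out as a group, so that the registry's figures come out too favourable. The documents do not support this. Anyone enrolled before or during cycle 1 stays in after one dose, Sections 2.1 and 4.3 admit the one-cycle stopper, and under those two sections the selection runs the other way. If all stoppers are already enrolled when they stop, there is no bias.

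It can also be said that the bracketed 2 cycles only defines a course and sets no minimum exposure. Section 4.5.2 uses it as a ceiling, and the one-dose threshold in the same bullet of 4.5.1 sits badly with a two-cycle minimum. This is probably what was intended. But the one-dose sentence limits whose data are used; it does not make an ineligible patient eligible. A site checking the criteria as written, which Section 4.7.2 lists among the baseline items, has no limb for this patient.

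A further inference would be that the imaging clause adds to the bias because early stoppers are scanned sooner. Nothing in the protocol says so. Section 4.7.2 puts the usual first assessment about three months after the start of therapy, and the clause does useful work by preventing entry once response is known.

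The screening log in Section 4.2 helps in part. It records patients who were approached and did not enter, but a patient judged ineligible and never approached may leave no entry.

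**Conclusion.** The protocol contradicts itself on who may enter the prospective cohort late, and 4.5.1 leaves a not-yet-enrolled one-cycle stopper without a place. This should be corrected, because late entry then depends on treatment progress, which the registry reports.

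Where 4.5.1 is applied literally, the distortion would tend to be favourable; where 2.1 and 4.3 are applied, it would tend the other way. The documents give neither the stopping share nor the share approached late, so the net direction and size are unknown. In the 20% illustration for literal use of 4.5.1, the response rate moves by 0 to 3 points, with 1.3 points at half approached late. The one-cycle share is more sensitive: 11.1% reported against 20% in that same case. All of these rest on assumed inputs.

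**What to change.** Reconcile 2.1, 4.3, 4.5.1 and 4.5.2 into one entry rule.

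- **4.5.1:** word the criterion as *is receiving, is expected to receive, or has received at least one dose of an initial course of HD IL-2 (up to 2 cycles, whether or not completed)*.
- **Imaging limit:** keep the requirement that enrolment come before post-treatment imaging. Replacing it with a day count from first dose could let patients in after response is known.
- **2.1 and 4.3:** give completers and early stoppers the same consent window, so that it does not close on completion of the course for some and stay open for others. Keep the Proclivity exception as a stated exception.
- **4.5.2:** refer to the same definition of a course.

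The cost is a wording amendment in four places and a few more patients with short treatment records; no visits or data items are added. The change does not address the separate matter that OS and PFS run from first dose while entry can come later.

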5.2 Patient Survival

Overall Survival (OS):

The OS is defined as the time from initiation of HD IL-2 treatment until patient death for any reason

Progression Free Survival (PFS):

PFS in this Registry is defined as the time from initiation of HD IL-2 treatment until disease progression or death.

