5.3 Treatment Emergent Events

Treatment emergent events are defined as changes in specific features occurring during and shortly after HD IL-2 administration.

Treatment Emergent Mortality (TEM):

TEM is defined as patient death occurring from Day 1 of HD IL-2 administration until 2 weeks after the last dose of HD IL-2.

Other treatment emergent events of interest will include, at a minimum, the following:

- Number of doses administered per cycle
- Cause(s) for concluding dosing each cycle
- Number of cycles administered
- Cause(s) for discontinuing HD IL-2 therapy

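### Prospective patients may enter after the first dose, under three conflicting entry rules, while TEM, OS and PFS run from the first dose, so TEM is biased down and OS up

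*Protocol*

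**What the plan says.** **Entry.** The protocol describes the prospective entry window three times.

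- Section 2.1: "sites will enroll patients who are expected to start a course of HD IL-2 therapy or have not yet completed their 1st course".
- Section 4.3: "Prior to completing their 1st course of HD IL-2, patients will be provided information about participation in the Registry and must sign" a consent form. Proclivity patients may sign at any time.
- Section 4.5.1: the patient "Is receiving or has received an initial course (2 cycles) of HD IL-2 and has not had post treatment imaging studies" before enrolment. Proclivity patients "can be enrolled into the registry at anytime".

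Section 4.7.2 places the first tumour assessment at about 3 months from the start of therapy, so the Section 4.5.1 window usually closes about then, except for Proclivity patients.

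**Consent.** Section 4.3: "Formal consent must be obtained before any prospective data collection occurs". Sections 4.4 and 12.2 repeat that consent comes before data entry. The screening log in Section 4.2 covers only patients who were approached.

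**Time origin.** Section 5.3: "TEM is defined as patient death occurring from Day 1 of HD IL-2 administration until 2 weeks after the last dose of HD IL-2". Section 5.2: "The OS is defined as the time from initiation of HD IL-2 treatment until patient death for any reason". PFS has the same origin. Section 6 puts OS and PFS in the annual report. The example query in Appendix A takes TEM as its primary endpoint, analyses all prospective patients without regard to when they consented, and hypothesises mortality below the historical rates of 2% (mM) and 4% (mRCC).

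**The concern.** A patient who dies of toxicity or rapid disease before anyone obtains consent leaves no record in the prospective cohort. A patient who consents later has, by definition, survived until then, yet is analysed as if observed from the first dose. This is left truncation handled as complete follow-up, also known as immortal time.

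For TEM the distortion is direct. A patient who consents more than two weeks after the last dose cannot become a TEM case unless treated again, but still counts in the denominator. OS gains guaranteed survival time. PFS is affected less outside Proclivity, because the no-imaging condition limits selection on imaged progression. What remains there is early death and clinical progression.

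At stake is a mortality rate that looks reassuring partly because of who could be enrolled. No later analysis can recover deaths that were never entered.

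**Working it through.** **1. The entry rules side by side**

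| Timing of consent | Section 2.1 | Section 4.3 | Section 4.5.1 |
|---|---|---|---|
| Before first dose | yes | yes | not named |
| During first course | yes | yes | yes |
| After the course, before imaging | no | no | yes |
| Proclivity patients | enrolled once dosed; no time limit given | any time | any time |

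A site cannot follow all three for a patient who has finished the course. The row for entry during the course shows that aligning Section 4.5.1 with the other two would shrink the problem but not remove it.

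**2. The plan's own figures (Appendix A, Section 8.1)**

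These are needed because the test below uses the stated N. Take a one-sample test against a fixed historical rate p0, expected rate p1, d = p0 − p1, two-sided alpha 0.05, 80% power, with continuity correction:

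n0 = [(1.960·√(p0(1−p0)) + 0.842·√(p1(1−p1))) / d]²; n = (n0/4)·[1 + √(1 + 2/(n0·d))]²

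- mM, 2% against 1%: n0 = 1282.6, n = 1380.8, so 1381.
- mRCC, 4% against 1%: n0 = 243.2, n = 275.5, so 276.
- With 20% dropout: 1381/0.8 = 1726.25, so 1727; 276/0.8 = 345; total 2072.

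All stated numbers reproduce. The point does not depend on N being wrong.

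**3. Effect on a test of TEM when mortality has not improved**

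Assumptions made here, not in the protocol:

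- an exact binomial test with lower tail 2.5%;
- m, the share of TEM risk that falls before consent. If a share f of patients consent late, after a share t of their risk has passed, m = f·t.

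Critical values:

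- mM: P(X ≤ 17 | 1381, 0.02) = 0.0201 and P(X ≤ 18) = 0.0336, so the claim is made at 17 deaths or fewer.
- mRCC: P(X ≤ 4 | 276, 0.04) = 0.0133 and P(X ≤ 5) = 0.0340, so the claim is made at 4 or fewer.

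The observed rate is q = p0(1 − m). The chance of a false claim is P(X ≤ c | N, q).

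| m | example | mM q | mM false claim | mRCC q | mRCC false claim |
|---|---|---|---|---|---|
| 0 | none late | 2.0% | 2.0% | 4.0% | 1.3% |
| 5% | 10% late, half of risk gone | 1.9% | 3.6% | 3.8% | 2.0% |
| 10% | 20% late, half gone | 1.8% | 6.2% | 3.6% | 2.8% |
| 25% | 50% late, half gone | 1.5% | 24% | 3.0% | 8% |
| 50% | all late, half gone | 1.0% | 84% | 2.0% | 35% |

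Removing the missed deaths from the denominator as well, q = p0(1 − m)/(1 − p0·m), changes little: at m = 50% the results are 83% and 33%.

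At m = 50% the mM rate falls to 1%, the whole effect the query plans to detect. For mRCC, reaching 1% would need m = 75%.

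**4. Effect on OS**

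Under exponential survival, the median from first dose among patients known to have survived a delay is the true median plus that delay. With a true median of 8.8 months (top of the melanoma range in Section 1.1), if every patient entered 1 to 2 months late the reported median would be 9.8 to 10.8 months. With no late entry it stays at 8.8. Universal late entry is an extreme case.

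**The case against.** **TEM is not the registry's main endpoint.** This stands. The primary objective (Section 3.1) is to build a data source. TEM is one metric in Section 5 and is not listed in the annual summary. The hypothesis and sample size appear only in an example query. But the entry rule governs every query, and OS and PFS are reported annually.

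**The remedy belongs in an analysis plan.** This stands in part. Delayed entry for OS and PFS could be set in an SAP that is not at hand, and its absence from the protocol is not the complaint. The entry rule is protocol content, and Appendix A fixes the TEM population as all prospective patients.

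**A reader might infer that Section 4.5.1 shuts out patients who have not started treatment.** The documents do not support this. Section 2.1 enrols those expected to start, and Section 4.3 holds back data entry until one dose has been given. The wording of Section 4.5.1 is loose and needs correcting.

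**A reader might infer that a patient who dies before consenting can never enter.** That is too absolute. Sections 4.3 and 12.2 let a legal representative sign. The documents do not say whether this extends to patients who have died, and nothing directs sites to use it so.

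**The net direction in the historical comparison may differ.** The historical rates are for treatment-related death. Section 5.3 counts every death in the window, while Appendix A adds physician-determined causality. Counting all deaths would raise TEM against that benchmark and could offset part of the bias.

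**Late entry may be rare.** Possible. The low rows of the table show little effect.

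**Conclusion.** The concern holds in this form. Sections 2.1, 4.3 and 4.5.1 contradict one another, which needs no assumption to establish. All three allow entry after the first dose. With consent required before data entry and no provision for earlier deaths, TEM is biased down and OS up, with a smaller effect on PFS outside Proclivity. The Proclivity exception is the widest route for late entry.

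The size is not known. Over an assumed 5% to 50% of TEM risk falling before consent, the chance of a false claim of lower mortality runs from 3.6% to 84% for mM and from 2.0% to 35% for mRCC. That spans negligible to severe and rests on the exact test assumed here.

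It would go too far to conclude that the entry rule alone would produce a positive result. Only the larger shares come near that, and the all-deaths count may pull the other way.

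**What to change.** - Reconcile Sections 2.1, 4.3 and 4.5.1 into one entry rule that names patients before the first dose and states how Proclivity entrants are handled.
- Define the TEM analysis set as patients consented on or before the first dose. Report later entrants, including late Proclivity entrants, separately.
- For OS and PFS, keep the first dose as time zero and let patients join the risk set at their consent date (left truncation), in Kaplan-Meier estimates and any Cox model.
- Report how many patients consented before the first dose, during the course and after it. This replaces the assumed shares above with facts.

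Cost: protocol wording and one analysis-set definition. Informed consent is a baseline item in Section 4.7.2, and the first-dose date is a listed feature in Appendix A, so the dates should already be available. The TEM set will be smaller and the estimate less precise. By how much cannot be said without the consent-timing counts. TEM and OS may look slightly less favourable.
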